### 2.3.2 Pre-Study Period: None

### 2.3.3 Subject Screening, Enrollment, and Consent Process:

Screening and informed consent will occur at Barnes-Jewish Hospital, following ECT referral by staff psychiatrists.

### 2.3.4 Inclusion/Exclusion Criteria

**Inclusion criteria:** Referral for ECT via right unilateral stimulation for treatment-resistant non-psychotic unipolar or bipolar depression, English-speaking, at least 18 years old, able to provide written informed consent.

**Exclusion criteria:** Known brain lesion or neurological illness that causes cognitive impairment, schizophrenia, schizoaffective disorder, blindness or deafness that may impair performance for cognitive testing battery, inadequate seizure duration with etomidate, defined at our institution as bilateral spike-and-wave complexes present for less than 10 seconds.

#### 2.3.5 Study Involvement

The randomized, crossover design of the study is powerful, as it will allow several within-patient comparisons, which will provide optimal efficiency to address the hypotheses. Specifically, the design will allow us to distinguish between the effect of ketamine anesthesia alone versus the combined effect of ketamine plus ECT. Recovery of consciousness after etomidate is generally rapid. Therefore, the etomidate plus ECT arm should yield additional insights into the contribution of seizures in the form of ECT to impaired consciousness and cognition and provides an additional comparator condition to the ketamine + ECT arm. Intra-patient repetition of each of the three exposures over two weeks will help to establish the reproducible effect of each exposure on the outcomes of interest.

### 2.3.6 Randomization and Blinding

A trained team member will use a computer-generated randomization algorithm among 18 potential combinations of initial cognitive task and order of study interventions. Random assignments will account for investigator-physician availability for ketamine + sham ECT sessions. The patient will be blind to the order of treatment condition. Study and clinician teams will be aware of the treatment arm at each session and maintain blinding by maintaining consistency of routine checks and monitoring before and after anesthetic induction. Thus, for all treatments sessions, patients will not be able to view the syringe during anesthetic induction. Furthermore, stimulation electrode and conducting gel will be placed on the scalp following loss and prior to return of consciousness. Post-anesthetic evaluation by anesthesiology, psychiatry, and nursing staff will be consistent across sessions.

To maximize study rigor and reproducibility, investigators evaluating study measurements for data quality and development of analytical tools will be blinded to details of the treatment intervention, whenever possible(Nuzzo 2015).

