#### **2.4.7.1 Outcomes** (Further details on instruments are provided in appendices)

#### Primary and Secondary Outcomes

Primary outcomes include: the temporal recovery profiles for cognitive task performance, as measured using the Cognition assessment battery (Basner, Savitt et al. 2015); times for the return of responsiveness to auditory command; and the presence of delirium, evaluated through the 3-Minute Diagnostic Assessment for CAM-defined delirium (3D-CAM)(Marcantonio, Ngo et al. 2014).

Secondary outcome measures based on the EEG will include definitions of the seizures by standard techniques using both expert reader interpretation and quantitative techniques (Haider, Esteller et al. 2016). Central seizure duration will be visually determined by clinician evaluation of the frontal-mastoid bipolar EEG ictal complexes. Additional measures will be calculated from windowed analyses of the high-density EEG: power spectral measures of the interval between anesthetic induction to delivery of ECT stimulus charge; the seizure envelope for 1-12 Hz EEG power; peak-to-peak amplitude, calculated from the difference in maximum and minimum voltages within 300 millisecond time; periodicity of epileptiform discharges; inter-hemispheric symmetry of seizure discharges; intra- and inter-hemispheric coherence. When possible, these measures and power spectral estimates will be derived different phase of the ictal waveforms(Gerst, Enderie et al. 1982). The following postictal EEG measures will be assessed: duration of postictal EEG suppression; power spectral parameters flanking the return of responsiveness to verbal command; power spectral parameters from eyes open and closed epochs, including assessments of the posterior dominant rhythm. Spatiotemporal analyses will also focus on the propagation of EEG signatures during the ictal and early postictal period.

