#### 2.5.1 Statistical Analysis

We will employ mixed-effects models to quantify trajectories of cognitive recovery over time while addressing inter-subject variance and missing data. Linear models with appropriate transformations will be used preferentially over non-linear models. Time and treatment intervention group will be included as fixed effects while random effects will account for repeated measures provided by each participant. Day of treatment relative to the dose-charge titration session will allow consideration of cumulative effects of treatment order that may remain biased despite randomization. To address differences in ECT-stimulation responsiveness, regression approaches will account for dose charge, central seizure duration, and age. Models will assess for the effects of treatment on the timing for the return of responsiveness to verbal command and the presence of delirium. Separate mixed-effects models will be generated to assess task performance in a group of young healthy volunteers during the recovery from isoflurane general anesthesia (Maier, McKinstry-Wu et al. 2017).

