Visualization and analyses of epileptiform EEG activity will be performed using Net Station and Persyst software (Persyst, Solana Beach, CA, USA), following interpolation of bad channels and re-referencing to the average signal. EEG dipole source localization, inter-hemispheric generalization, and phase-reversals will be assessed by epilepsy board-certified neurologists. Seizures will be staged according to the previously described three components of electrical seizures induced by ECT (phase I with initial 14-22 Hz rhythmic beta activity, phase II with arrhythmic polyspike activity, and phase III with rhythmic 2.5-3.5 Hz. spike/polyspike activity(Gerst, Enderie et al. 1982). Additionally, expanding on previous analyses of stationarity in epileptiform activity induced by ECT(Zoldi, Krystal et al. 2000), we will use high-density EEG to topographically map rhythmic sharp-wave discharges. To maintain rigor, evaluators will be blinded to the study intervention.

Structural MRI scans, including T1-weighted images will be used for source localization using Brainstorm software.

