# End of Patient Interview

#### Thank you so much for your time.

Proceed to area for completion of interview observation items and final coding.

Used with permission. The SAGES Study: Training Manual and Questionnaires; 2010; Boston, Aging Brain Center.

OBSERVATIONS	FEATURE 4 IS
	PRESENT?
11A. Was the patient sleepy during the interview? (requires that they actually fall asleep, but is easy to arouse)	1 – No 2 - Yes
	FEATURE 4 IS
11B. Was the patient stuporous or comatose during the interview? (Difficult to impossible to arouse.)	PRESENT?
()	1 – No 2 - Yes
12. Did the patient show hypervigilance such as excessively strong	FEATURE 4 IS
responses to ordinary objects/stimuli in the environment, being	PRESENT?
inappropriately startled, etc.?	1 – No 2 - Yes
13. Was the patient's Flow of ideas unclear or illogical, for example saying	FEATURE 3 IS
something non-sensical, unrelated to the interview (tangential) or making	PRESENT?
contradictory statements	1 – No 2 - Yes
14 Convergetion republing for every le did he abe sive incorrection	FEATURE 3 IS
14. Conversation rambling , for example did he/she give inappropriately verbose and off target responses?	PRESENT?
verbose and on target responses:	1 – No 2 - Yes
	FEATURE 3 IS
15. Was the patient's speech unusually limited or sparse ? (e.g. yes/no	PRESENT?
answers) or unusually slow or halting ?	1 – No 2 - Yes
16. Did the patient have trouble keeping track of what was being said	FEATURE 2 IS
during the interview, for example, fail to follow instructions or answer	PRESENT?
questions one at a time?	1 – No 2 - Yes
17. Did the patient fail to attend to the interview due to being	FEATURE 2 IS
inappropriately distracted by environmental stimuli, for example, respond	PRESENT?
to questions asked of roommate?	1 – No 2 - Yes
10. Did the notional level of consciousness fluctuate during the interview	FEATURE 1 IS
18. Did the patient's level of consciousness fluctuate during the interview, for example, start to respond appropriately and then drift off?	PRESENT?
for example, start to respond appropriately and then drift on?	1 – No 2 - Yes
19. Did the patient's level of attention fluctuate during the interview, e.g.,	FEATURE 1 IS
did the patient's focus on the interview or performance on the attention	PRESENT?
tasks (digit span, days & months backwards) vary significantly?	1 – No 2 - Yes
	FEATURE 1

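### 3D-CAM delirium, a primary outcome, has no masked rater, so a ketamine + ECT versus ketamine + sham difference in delirium could partly reflect rater expectation

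*Combined protocol and SAP*

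**What the plan says.** Section 2.4.7.1 lists among the primary outcomes "the presence of delirium, evaluated through the 3-Minute Diagnostic Assessment for CAM-defined delirium (3D-CAM"). Section 2.5.1 adds: "Models will assess for the effects of treatment on the timing for the return of responsiveness to verbal command and the presence of delirium".

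On masking, section 2.3.6 covers the patient ("The patient will be blind to the order of treatment condition") and says of the staff: "Study and clinician teams will be aware of the treatment arm at each session". Two further statements concern other people. Section 2.3.6 says that "investigators evaluating study measurements for data quality and development of analytical tools will be blinded to details of the treatment intervention, whenever possible". Section 2.5.4, in its account of reading the epileptiform EEG, says: "To maintain rigor, evaluators will be blinded to the study intervention".

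The 3D-CAM form in the Appendices has a blank for the evaluator but gives no role or masking status. Items 1 to 10 are answered by the patient: orientation, attention tasks and reported symptoms. The rater then completes observation items, for example "Was the patient sleepy during the interview" and "Did the patient have trouble keeping track of what was being said". The form diagnoses delirium when features 1 and 2 are present together with feature 3 or 4.

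**The concern.** Masking is provided for EEG readers, and where possible for those who check data quality or build analytical tools. It is not provided for the person who generates a primary outcome at the bedside. The protocol also tells that person what to expect. Section 2.5 proposes that the features after ECT will resemble postoperative delirium, and section 2.5.2 expects cognition to recover most slowly after ketamine + ECT.

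The Cognition battery is computerised and much less open to this influence. The 3D-CAM is not. If drowsiness, slow speech or drifting attention is coded more readily in sessions known to include ECT, the delirium comparison mixes a treatment effect with a rating effect, and nothing in the plan separates them.

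**Working it through.** **Is the outcome covered by any masking provision?** There are three statements. The patient is blind to the order of treatments (2.3.6). Those reviewing data quality and developing analytical tools are blinded where possible (2.3.6). The evaluators in the EEG section are blinded (2.5.4). None names the 3D-CAM rater. That this rater knows the arm is an inference from the general sentence on the study and clinician teams, together with the absence of any exception.

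**How much of the score is observer judgement?** From the coding summary on the form:

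| Feature | Patient-answered items | Observer items |
|---|---|---|
| 1 Acute onset, fluctuation | 8, 9, 10 | 18, 19, 20 |
| 2 Inattention | 4, 5, 6, 7 | 16, 17 |
| 3 Disorganized thinking | 1, 2, 3 | 13, 14, 15 |
| 4 Altered consciousness | none | 11A, 11B, 12 |

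Observer ratings: 3 + 2 + 3 + 3 = 11. One positive item is enough for a feature.

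**Can one impression decide the diagnosis?** Yes, in some sessions. Suppose the patient makes an attention error (feature 2) and reports confusion (feature 1), but is fully oriented. One tick for sleepiness then sets feature 4 and completes the diagnosis. If feature 1 is absent, the same tick opens items 21 and 22. Item 22 allows feature 1 to be set from any newly positive item against earlier ratings, and a baseline 3D-CAM precedes every treatment. A negative score also ends further 3D-CAM testing that day (Appendices, Post-treatment), so one rating decides whether later ones are made.

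**What is the relevant denominator?** Section 2.3.1 gives six experimental sessions per patient, two per condition. With 15 to 20 patients that is 15 × 2 = 30 to 20 × 2 = 40 sessions per condition. One reclassified session moves a condition's rate by 1/40 = 2.5 to 1/30 = 3.3 percentage points.

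**Can the size be computed?** No. The documents give no 3D-CAM rate, no rater error and no power for delirium. Section 2.6 concerns minutes of cognitive recovery, so the plan has no delirium figure to reproduce. The 5-12% in section 2.1.2 is a share of patients with agitation and disorientation. It is neither a per-session rate nor a 3D-CAM rate.

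**Illustration, on assumptions only.** Let the true rate p be equal in both ketamine conditions, and let a share b of non-delirious ketamine + ECT sessions be scored positive because the arm is known. The coded rate under ketamine + ECT is p + (1 − p)b; for p = 0.05 and b = 0.10 this is 0.05 + 0.95 × 0.10 = 0.145. Sessions are treated as independent. The chance that a two-sided 0.05 pooled z test rejects was found by enumerating both binomial counts. The 5% and 12% rates borrow the section 2.1.2 range; 30% and all values of b are assumed.

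| p | b | Coded rate, ketamine + ECT | Rejects, n = 30 | Rejects, n = 40 |
|---|---|---|---|---|
| 5% | 0 | 5.0% | 2.8% | 4.3% |
| 5% | 10% | 14.5% | 24.6% | 32.6% |
| 5% | 20% | 24.0% | 59.9% | 72.9% |
| 12% | 0 | 12.0% | 5.5% | 5.7% |
| 12% | 10% | 20.8% | 15.0% | 18.9% |
| 12% | 20% | 29.6% | 38.9% | 50.5% |
| 30% | 0 | 30.0% | 4.9% | 4.8% |
| 30% | 10% | 37.0% | 8.5% | 9.8% |
| 30% | 20% | 44.0% | 19.7% | 25.4% |

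**Aim 3.** Here delirium is a predictor of cognitive recovery. Section 2.5.1 includes treatment as a fixed effect. Within an arm, miscoding driven by knowledge of that arm should be largely unrelated to a computerised score. It adds error to the predictor and would more likely weaken the association than create it.

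**The case against.** The strongest reply is that the patient's own answers may settle most diagnoses. Items 1 to 10 can supply features 1, 2 and 3 without any observer item, and one wrong answer is enough for feature 2 or 3. Just after responsiveness returns, such errors may be common, which leaves the observer items less room to tip the result. This stands. It limits the concern to part of the score, but the form still lets an impression decide in the remaining sessions.

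A second reply is that the study is described as exploratory, that section 2.5.2 analyses delirium for its association with cognitive recovery, and that no directional hypothesis compares delirium between arms. All of that is true. Delirium is nevertheless a declared primary outcome, and section 2.5.1 models the treatment effect on it.

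Three stronger readings are tempting and are not supported:

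- A reader might infer that the protocol gives the 3D-CAM to an unmasked research rater. It does not say who the rater is.
- A reader might size the bias by applying 5-12% to all 60 to 80 ECT sessions. That pools etomidate + ECT into a contrast with only 30 to 40 ECT sessions, and it applies a per-patient rate for a different event to sessions.
- A reader might conclude that Aim 3 inherits the same upward bias. With treatment in the model, attenuation is more likely.

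**Conclusion.** The concern holds in limited form. As written, the plan leaves a primary outcome that rests partly on observer judgement without a masked rater, so a ketamine + ECT versus ketamine + sham difference in delirium could partly reflect expectation. This rests on the inference that the unnamed 3D-CAM rater belongs to the teams described in section 2.3.6. The documents do not show that such bias will occur or how large it would be. The tabulated figures show only what assumed miscoding rates would do, and the effect shrinks as the true rate rises. The point does not extend to the computerised battery, and it does not imply a spurious association in Aim 3. It merits a change because the analysis remedy uses item-level data already on the form.

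**What to change.** **(a) Analysis.** Pre-specify a sensitivity analysis of the treatment effect on delirium that uses patient-answered items only: feature 2 from items 4 to 7, feature 3 from items 1 to 3, and feature 1 from items 8 to 10 or from item 22 restricted to new errors on items 1 to 10 against that session's baseline 3D-CAM. Item 22 is worded by day of hospitalization, so the plan should say that it is applied this way to outpatient sessions. Report both estimates with confidence intervals. Describe an effect seen only when the observer items are included as possibly due to unmasked rating. Do not require the two versions to agree in direction before claiming an effect: they share items, so agreement is partly built in, and with few events the restricted version may have no direction.

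**(b) Conduct.** Where existing staffing allows, assign the 3D-CAM to a team member who is absent until responsiveness returns and is not told the arm, and record that rater's guess of the arm. Masking may be imperfect, because testing takes place in the room used for treatment and sham sessions depend on physician availability. If this cannot be done, state unmasked rating as a limitation.

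**Cost.** Part (a) needs one further model and tabulation. Part (b) needs a reassignment of tasks and one added field. The restricted version omits feature 4 and items 11 to 20, so it will find fewer cases. Items 8 to 10 ask about the past day and may pick up recalled emergence symptoms. It therefore belongs beside the standard score and should not replace it.

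Before either definition is fixed, the Delirium Assessment paragraph in the Appendices, which accepts any three of the four features, must be reconciled with the algorithm on the form.

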#### 2.3.7 Interventions

Each patient will be included for seven sessions. As with all non-study patients, the first sessions consists of a dose-charge titration that is used to determine the current required to induce the seizure. At Barnes-Jewish Hospital, etomidate is commonly used to induce general anesthesia for this session. During four of the next six sessions, the patients will receive care that is currently within the standard of care for refractory depression, namely general anesthesia (standard of care or ketamine) plus ECT. In addition, during two sessions, patients will receive only general anesthesia with ketamine, which has now been shown to have efficacy in treating refractory depression. Apart from these treatments, patients will be monitored with full montage electroencephalography and will complete tests of cognition, mood and depression before and for approximately two hours following the general anesthesia (with or without ECT).

### 2.3.8 Observations and Measurements

#### **Dose-Charge Titration Visit (Visit 1)**

During the titration visit, the study team will assess baseline cognitive function and EEG prior to ECT, tolerability of cognitive testing and EEG recording. Patients will have baseline assessments, including a

cognitive battery (COGNITION), continuous electroencephalography, 5 minutes of resting state EEG with eyes open and 5 minutes for eyes closed, depression testing (PROMIS-CAT) and mood assessment (Self-Assessment Manikin), suicidal ideation (Scale of Suicidal Ideation)(Beck, Kovacs et al. 1979), and the 3D Confusion Assessment Method (3D-CAM) before the ECT therapy session .ECT charge will be delivered via a Thymatron System IV (Somatics, LLC, Venice, FL, USA). Per ECT laboratory procedures, stimulation parameters include current 0.9 amperes, pulse width of 0.3 milliseconds, with escalating dosage: (5% total charge: 24.9 millicoulombs, 10 Hz stimulation, 4.6 second duration; 10% total charge: 50.8 millicoulombs, 20 Hz stimulation, 4.65 second duration, 15% total charge: 75.6 millicoulombs, 20 Hz stimulation, 6.98 second duration). Subsequent planned ECT treatment is based on six-fold increase in charge delivery. Thus, individuals without suitable seizure duration at projected 100% charge will be withdrawn from the study.

### **Experimental Treatment Visits (Visit 2-7)**

Baseline assessments will be performed at each session immediately prior to ECT and will include a cognitive battery (COGNITION), electroencephalography, depression testing (PROMIS-CAT) and mood assessment (Self-Assessment Manikin), suicidal ideation (Scale of Suicidal Ideation)(Beck, Kovacs et al. 1979), and the 3D Confusion Assessment Method (3D-CAM). Details regarding these assessments are provided as an appendix at the end of the protocol.

During four of these six sessions, the patients will receive care that is currently within standard practice for ECT: general anesthesia (standard of care or ketamine), muscle paralysis (succinylcholine), and electrical stimulation. For the remaining two sessions, patients will undergo a ketamine general anesthetic without muscle paralysis or ECT stimulation.

High-density EEG, bilateral fronto-mastoid clinical EEG, and full American Society of Anesthesiologists (ASA) monitoring will commence prior to the induction of general anesthesia. Prior to induction, audible squeeze toys will be placed in each hand of the patient, who will be instructed to follow serial commands to either "Squeeze your left hand twice" or "Squeeze your right hand twice." Every 30 seconds, one of these commands will be played at random, to monitor loss and return of consciousness. Patients will be pre-oxygenated by mask and

11

anesthesia will be induced with ketamine, approximately 2 mg/kg, or standard of care. Following bolus of the induction agent, loss of responsiveness and evelash reflex will be confirmed. Loss of consciousness will be recorded as the first time when a subject fails to correctly respond to the command. Care adherent to the ASA guidelines will be performed regardless of treatment session. For sessions with ECT, pre-stimulation hyperventilation and assisted ventilation will also be performed. Central seizure duration will be assessed from bilateral fronto-mastoid EEG by the psychiatry team. Peripheral seizure duration will be determined through monitoring of tonic-clonic activity (Fink and Johnson 1982). During the sessions that subjects receive ECT, other drugs will also be administered according to current practice and as clinically indicated. The return of eye opening will be assessed every 30 seconds and defined for the initial time at which the patient opens his eves to verbal command. The ability to extend the thumb to verbal command ("thumbs up") will be assayed every 30 seconds. Return of responsiveness to auditory command will be defined as the first time at which the patient has squeeze his correct hand the number of times instructed via auditory commands. At this time, defined as t = 0 minutes, the subject will begin a series of cognitive and behavioral assessments, which are repeated every 30 minutes up to two hours after return of responsiveness. Patients will be permitted to take brief breaks to use the restroom and eat or drink, as necessary. At the conclusion of each treatment session, depression testing (PROMIS-CAT) and mood assessment (Self-Assessment Manikin) will be performed to assess for early improvements in mood. To assess blinding quality, the patient will be asked their impression of whether they received ECT that day. They will be discharged according to standard post-anesthesia care unit discharge criteria upon completing the last neurocognitive test battery. A study site coordinator will contact each subject within 24 hours of the study day to assess and document any adverse events.

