### 2.5.2 Primary Analyses:

Recovery of Responsiveness: Given that the induction of generalized seizures by electrical stimulation may compound the recovery from general anesthesia, we expect that interval from loss to return of responsiveness following ketamine + ECT will be longer compared to the period for ketamine + sham ECT. We will determine the median and 95% confidence intervals for this measure in relation to the treatment intervention.

Recovery of Cognition: Given that postictal suppression may be prolonged with ketamine than with etomidate(Hoyer, Kranaster et al. 2014), we hypothesize that the time needed for the return of cognition to baseline on individual sessions will be greatest for ketamine + ECT, followed by etomidate + ECT, and ketamine + sham ECT. Separate mixed-effects models will be generated based on reaction time and accuracy. We will determine the time of convergence for 95% confidence intervals for the marginal responses related to

the three treatment groups. To determine the timing for the recovery to baseline, we will determine the time when the same 95% confidence intervals include 0.

Postictal Delirium and Cognitive Recovery: We expect the incidence of delirium (3D-CAM) to be associated with delayed restoration of baseline function in all cognitive domains. The magnitude and significance of this relationship will be determined from the mixed effects models for each cognitive test.

Comparison of Cognitive Recovery After ECT and Isoflurane General Anesthesia: We hypothesize that the time for recovery to baseline will be quicker for treatments involving ECT compared to that for the recovery from isoflurane general anesthesia. Convergence for 95% confidence intervals will be compared between treatment groups.

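### Paralysis and seizure always occur together in this design, so a longer time to a hand squeeze after ketamine + ECT measures the whole ECT procedure and cannot be credited to the seizure alone

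*Combined protocol and SAP*

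**What the plan says.** Section 2.3.8 (Experimental Treatment Visits) describes the four ECT visits as "general anesthesia (standard of care or ketamine), muscle paralysis (succinylcholine), and electrical stimulation". For the other two visits, "patients will undergo a ketamine general anesthetic without muscle paralysis or ECT stimulation". The same section describes hyperventilation before the stimulus, and assisted ventilation, only for sessions with ECT.

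The endpoint is defined there too: "Return of responsiveness to auditory command will be defined as the first time at which the patient has squeeze his correct hand", to commands played every 30 seconds. The other bedside signs are eye opening on command and "The ability to extend the thumb to verbal command". The squeeze also sets t = 0 for the cognitive batteries.

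Section 2.4.7.1 lists "times for the return of responsiveness to auditory command" among the primary outcomes. Section 2.5.2 expects that the "interval from loss to return of responsiveness following ketamine + ECT will be longer compared to the period for ketamine + sham ECT", and gives this reason: "Given that the induction of generalized seizures by electrical stimulation may compound the recovery from general anesthesia". The general hypothesis in section 2.2 makes the rate and order of recovery depend on whether a seizure was induced. Section 3.4 presents the study as showing what a seizure does to consciousness and cognition.

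**The concern.** A hand squeeze needs a working neuromuscular junction as well as a responsive brain. Eye opening and thumb extension are motor signs too, so they offer no independent check. If some block remains when the patient would otherwise have responded, the recorded interval in ECT sessions includes time during which a response was not possible. Nothing comparable can happen in the sham sessions.

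Two conclusions are at stake. For Aim 1, such a delay points the same way as the hypothesis and could be read as an effect of the seizure. For Aim 2, a later t = 0 in ECT sessions discards early recovery time from the cognitive clock, so recovery after ECT looks quicker than it was.

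**Working it through.** **The plan's own figures.** No sample size, difference or SD is stated for return of responsiveness. Section 2.6 concerns cognitive trajectories only. Its figure of 24 (difference 20 min, SD 20 min, power 80%) is close to n = 2[σ(z_α + z_β)/Δ]² with two-sided alpha 0.05/6 for the six pairs among four means. That gives 24.22, rounded up to 25. The present point does not depend on it.

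**Step 1: can the three conditions separate seizure from paralysis?** Coding from sections 2.3.1 and 2.3.8:

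| Condition | Ketamine | Seizure | Paralysis |
|---|---|---|---|
| Ketamine + sham | 1 | 0 | 0 |
| Ketamine + ECT | 1 | 1 | 1 |
| Etomidate + ECT | 0 | 1 | 1 |

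The last two columns are identical. The additive contrasts are:

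- Ketamine + ECT minus ketamine + sham = seizure + paralysis, together with stimulus and ventilation.
- Etomidate + ECT minus ketamine + sham = the same sum, plus the change of anesthetic.
- Ketamine + ECT minus etomidate + ECT = the change of anesthetic only. Paralysis is common to both and cancels if its effect is the same in each.

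No model fitted to these conditions can split the first sum.

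**Step 2: do the planned covariates help?** Section 2.5.1 adjusts for dose charge, central seizure duration and age. The first two are zero or undefined in sham sessions, and no relaxant term is named. The planned correlation of seizure duration with the interval (section 2.5.3) uses ECT sessions only, so it cannot remove a difference between ECT and sham. The documents describe no neuromuscular monitoring and no limb spared the relaxant.

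**Step 3: when is there bias?** Let C be the time at which the patient would respond without block, and B the time at which block allows a squeeze. The observed time is max(C, B), so the added time is max(0, B − C). It is zero whenever block ends first. The documents give neither quantity. Assuming B − C adds 0 to 5 minutes, the shift is 0 to 5 × 60/30 = 0 to 10 command checks.

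**Step 4: what could such a shift do?** This is an illustration with no seizure effect, a constant added delay b, a two-sided 5% paired t-test on patient means, and noncentrality b/(s/√n). The delay b and the SD s of the paired difference are assumptions, and the protocol does not plan this test. Rejection rates:

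| n | SD (min) | b = 0 | b = 1 | b = 2 | b = 5 |
|---|---|---|---|---|---|
| 15 | 5 | 5% | 11.2% | 30.3% | 94.9% |
| 15 | 10 | 5% | 6.5% | 11.2% | 43.8% |
| 15 | 20 | 5% | 5.4% | 6.5% | 14.7% |
| 20 | 5 | 5% | 13.6% | 39.7% | 98.9% |
| 20 | 10 | 5% | 7.1% | 13.6% | 56.5% |
| 20 | 20 | 5% | 5.5% | 7.1% | 18.6% |

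For example, with n = 15, SD 5 and b = 2, the noncentrality is 2/(5/3.873) = 1.55. The consequence runs from nothing to near-certain rejection, depending on two quantities the documents do not supply.

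**Step 5: the cognitive clock.** If cognition returns at time R after induction and the squeeze at S, the planned clock records R − S. A block delay b changes this to R − S − b, which is shorter by b in ECT sessions only. Against the 20 to 40 minute differences in section 2.6, 5 minutes is 5/40 = 12.5% to 5/20 = 25%. Against the 30-minute spacing of the batteries it is one sixth.

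**The case against.** The strongest reply is that Aim 1 already compares ketamine + ECT with ketamine + sham ECT, which is a comparison of procedures. Section 2.1.3 describes modern ECT as including paralysis. The planned output is a median with a 95% confidence interval by treatment, the rationale says only that seizures may compound recovery, and section 2.5 calls the study exploratory. In section 2.3.5 the claim that "the design will allow us to distinguish between the effect of ketamine anesthesia alone versus the combined effect of ketamine plus ECT" is likewise about the whole package and is not in error. All of this stands. A reader might infer that Aim 1 is invalid; the documents do not support that. What remains is the step from the contrast to the seizure, which sections 2.2, 2.5.2 and 3.4 do take. An exploratory label does not make the two causes separable.

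The second reply is that block may always end before the patient would respond. That is possible. A reader might infer that part of any observed delay is certainly neuromuscular, but without a duration of block the documents show neither bias nor its absence.

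Third, the shift in t = 0 is modest beside a battery lasting 15 to 20 minutes, and it works against the hypothesis that ketamine + ECT recovers slowest. This also stands: it could hide an Aim 2 effect but would not create one.

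Finally, a reader might think of restarting the interval at return of muscle function. That would not be sound. Sham sessions have no such event, so start points would differ by condition, and section 2.4.7.2 does not say that this time is recorded. With assumed values of 12 minutes for sham and 15 for ECT, and muscle function back at 6 minutes, the restarted ECT interval is 15 − 6 = 9. A true 3-minute delay would then appear as a 3-minute advantage.

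**Conclusion.** The concern holds as a limit on interpretation. Seizure and paralysis coincide in every condition, so the primary contrast estimates the effect of the whole ECT procedure and a longer interval cannot be assigned to the seizure alone. This follows from the design and needs no assumption.

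The size of any bias is unknown. It is zero if block never outlasts the unresponsiveness that would occur anyway. Under the assumed 0 to 5 minutes it is 0 to 10 command checks, lengthening the ECT interval as hypothesized and shortening apparent cognitive recovery by the same amount. Ketamine + ECT versus etomidate + ECT is much less exposed, since both include paralysis.

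**What to change.** Leave clinical care as it is and change three things in the plan.

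1. In sections 2.2 and 2.5.2, state that ketamine + ECT versus ketamine + sham estimates the effect of the ECT procedure as a whole (stimulus, seizure, paralysis and ventilation), and that a longer interval will not be attributed to the seizure alone. Carry the same wording into any report.
2. Repeat the cognition analysis with time counted from induction or from loss of responsiveness, either of which is defined alike in all conditions. Section 2.3.8 and Appendix 1 count loss differently (one missed command against two consecutive), so name the one used. Battery times will then differ between sessions, which a mixed model with continuous time can handle. This clock includes the time taken to deliver ECT, in keeping with the whole-procedure reading.
3. Report the EEG measures already planned around return of responsiveness (sections 2.4.7.1 and 2.5.4) as non-motor supportive evidence. They inform the interpretation but do not remove the confounding.

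The cost is a narrower stated claim and one additional analysis. No new data are needed.
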